ENDPOINTS:

Primary Endpoint

- One point decrease from baseline in target lesion Global PG (GPG) Severity Score at Week 16

Secondary Endpoints

- Complete re-epithelization of PG lesions (GPG Severity Score of 0) at visits 3, 4, 5, 6, 7, 8, and 9.
- Absolute change from baseline in patient-reported pain severity (Pain-VAS) at visits 3, 4, 5, 6, 7, 8, and 9 and at complete re-epithelization of ulcer.
- Absolute change in quality of life (DLQI) from baseline at visits 3, 4, 5, 6, 7, 8, and 9 and at complete re-epithelization of ulcer.
- Recurrence of PG lesions after complete re-epithelization (GPG score 0) of all lesions and spesolimab cessation

- Time to worsening (1 or more GPG point increase) of target PG lesion from spesolimab cessation

STUDY DESIGN OVERVIEW:

This study is a prospective, proof-of-concept, open label clinical trial. The study will take place at Icahn School of Medicine at Mount Sinai.

The study will screen up to 25 subjects in order to enroll a total of up to 20 patients with at least one clinically measurable ulcerative PG lesion. Subjects will receive 900 mg of spesolimab intravenously (IV) over 90 minutes at a frequency of every 4 weeks until Week 28 with the following exceptions:

- At the Week 8 visit, subjects who do not show any improvement, show only minimal improvement, or those that begin to lose their initial improvement response (decrease in pain or wound drainage), may be switched to a dosing frequency of every 3 weeks through Week 26, at the discretion of the investigator. These subjects will still return at Week 16 for an endpoint visit, but will not receive treatment at this visit. Refer to Tables 3 and 4 for schedule of events.

All subjects will be monitored monthly for 4 months subsequent to treatment cessation.

Subjects who reach GPG score 0 at anytime during the study will continue to receive treatments until week 28 (or Week 26 depending on dosing frequency) and will then be monitored for 4 months subsequent to treatment cessation.

Subjects who are experiencing improvement in their PG but who have not reached complete wound healing will continue treatment until Week 28 (or Week 26 for those who were switched to every 3 week dosing), even if primary endpoint has been achieved. These subjects will then be monitored for 4 months subsequent to treatment cessation.

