Contraindications to spesolimab treatment include patients with severe or life-threatening hypersensitivity to spesolimab or to any of the excipients in spesolimab¹⁴. In our experience, patients infused with spesolimab exhibited no adverse reactions during or after treatment with no pre-medication required. There is limited data available on the impact of antidrug antibodies on safety and efficacy upon retreatment. Furthermore, it is not known whether spesolimab increases or decreases the efficacy of other medications.

PRIOR TREATMENT:

All relevant treatment received by the subject within 30 days before screening will be recorded.

CONCOMITANT TREATMENT:

Concomitant medications are permitted for the treatment of stable, chronic illness as well as for pyoderma gangrenosum. Concomitant treatments for pyoderma gangrenosum will tapered over spesolimab treatment course as tolerated. Use of such concomitant medication or other medications that may be required throughout the study will be recorded (including the reason for treatment and name, dose, unit, route, and the date of treatment as appropriate) until treatment termination and throughout follow-up period. Patients will be allowed to continue with biologic therapies used to treat comorbidities.

PROHIBITED TREATMENT:

All treatments prohibited by clinician during the screening period are also prohibited throughout the course of the study. No live attenuated vaccinations are permitted throughout the study.

PROCEDURES:

Monitoring of AEs will begin at the time of signing the informed consent form and will be continued throughout the course of the study. All study procedures will be completed at designated times during the study period (see Tables 3 and 4). Subjects will receive 900mg IV spesolimab at a frequency of every 4 weeks through Week 8, at which time, at the discretion of the investigator, dosing frequency may be increased to every 3 weeks. Subjects will continue to dose every 4 or 3 weeks through Week 28 or 26 (depending on

dosing frequency). Subjects will be monitored once a month, for 4 months after treatment cessation. Patients that, in the opinion of the investigator, are benefiting from treatment at week 28 but need more therapy to achieve wound closure may be eligible to continue on treatment (on case-by-case basis) to a maximum of 52 week after discussion with Boehringer Ingelheim trial team.

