Subjects are numbered sequentially. Each subject screened (total of 25 screened) will be assigned a unique screening number for the duration of the study. Subject screening numbers will also become a subjects treatment number if they are enrolled in the study after providing informed consent and meeting inclusion criteria. Subjects who discontinue or withdraw from the study before receiving a treatment assignment code, but re-enroll at a later time must be assigned a new screening number. The investigator must maintain a master log linking the subject number to the subject's name. The investigator must follow all applicable privacy laws in order to protect a subject's privacy and confidentiality.

INVESTIGATIONAL DRUG SUPPLY :

Eligible participants will receive 900 mg intravenous spesolimab starting at Visit 2/week 0/Baseline. All participants will receive a total of 8 or 9 infusions (depending on dosing frequency) through Week 28 or Week 26 (depending on whether the subject's dosing frequency is increased to every 3 weeks at Week 8), unless there is significant worsening. All subjects should be observed for 30 minutes following the infusion at Baseline to assess safety. Select cases will be offered the opportunity to continue treatment through Week 52 on case-by-case basis if the patient would benefit from continued treatment. All subjects who have not been discontinued will be monitored once a month, for 4 months after treatment cessation.

All study medication will be provided by Boehringer Ingelheim, refrigerated and stored between 2-8°C in a secure area. Study drug will be administered to subjects at each study visit in office. The investigative site will account for all study drug dispensed and stored during the study.

STATISTICAL CONSIDERATIONS:

Sample Size

This is a proof-of-concept, open-label trial. Twenty patients will be enrolled in the trial to demonstrate efficacy of spesolimab in a population of patients with moderate-severe, refractory PG. Although there is no formal power calculation, a sample size of n=20 subjects allows 81% power at 2.5% significance for a one-sided binomial test to detect at Week 16 a difference of 36.6% in the proportion of GPG success compared to a constant set to be equal to 10%. The choice of the constant was based on data from a randomized clinical trial for efficacy of infliximab where a group of 17 PG placebo-treated patients showed 6% response at Week 2 (Brooklyn et al.,2006).

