Demographics and Other Baseline Characteristics

Descriptive statistics of demographics and other baseline characteristics of patients will be summarized with mean, median, and standard deviation for quantitative outcomes, and frequency and percentage tables for categorical outcomes.. Other baseline characteristics include sex, age, height, weight, vital signs, duration of PG, history of pathergy or PG trigger (if known), concurrent diagnoses from medical history and indications for concomitant medication, concomitant medication, and previous PG treatments.

Target Lesion Measurement and Digital Image Assessments

Size of target PG lesion will be approximated at each visit by measuring the length, width and depth of the lesion. Target lesion will also be analyzed using Image J software to obtain a more precise surface area of each lesion using digital photographs taken at each visit.

Analysis of Primary Endpoint

We will compare the proportion of patients achieving one-point decrease in target lesion GPG score at Week 16 with a constant p=0.10. Clopper-Pearson 90% confidence interval will be estimated.

Analysis of Secondary Endpoints

- One sided Clopper-Pearson 90% confidence intervals will be estimated for the proportion of patients achieving re-epithelization (GPG Severity Score of 0) at Visits 3, 4, 5, 6, 7, 8, and 9
- We will apply a two-sided paired t-test to evaluate significance of the mean difference of GPG score at Week 16 versus Week 0.
- Mean patient reported scores of pain (Pain VAS) and quality of life (DLQI) at baseline will be compared to those at Week 16 and treatment termination using the student's t- test to compare between subject's pre and post-treatment scores.
- One sided Clopper-Pearson 90% confidence intervals will be estimated for the proportion of patients with recurrence or worsening of PG lesions from point of complete re-epithelization or spesolimab cessation at end of treatment visit (Week 28 or Week 26 depending on dosing frequency).

Interim Analysis

An interim analysis will be performed after the first 10 subjects complete Week 16. We will continue enrollment during this time. Proportion of patients achieving one-point GPG score decrease will be reported. Changes from baseline at Week 16 in the PG lesions (number, size, GPG score) will be evaluated and reported. Enrolled subjects will continue to receive treatments during this time.

Data Transfer and Management

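### Time to worsening after stopping spesolimab has no time-to-event analysis, and the planned recurrence-or-worsening proportion starts at a point that conflicts with the recurrence endpoint

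*Combined protocol and SAP*

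**What the plan says.** ENDPOINTS, Secondary Endpoints, lists two off-drug outcomes:

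- The first is an occurrence: "Recurrence of PG lesions after complete re-epithelization (GPG score 0) of all lesions and spesolimab cessation".
- The second is a duration: "Time to worsening (1 or more GPG point increase) of target PG lesion from spesolimab cessation".

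STATISTICAL CONSIDERATIONS, Analysis of Secondary Endpoints, has one line that covers them. It plans one-sided 90% Clopper-Pearson intervals on this quantity: "proportion of patients with recurrence or worsening of PG lesions from point of complete re-epithelization or spesolimab cessation at end of treatment visit". That visit is then given as Week 28 or 26, according to schedule. The line gives no time-to-event method, censoring rule, denominator or evaluation time.

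Three other provisions bear on the point:

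- **Treatment after healing.** STUDY DESIGN OVERVIEW says: "Subjects who reach GPG score 0 at anytime during the study will continue to receive treatments until week 28" (Week 26 on the three-weekly schedule).
- **Extension.** PROCEDURES says that subjects who are benefiting but not yet closed "may be eligible to continue on treatment (on case-by-case basis) to a maximum of 52 week". INVESTIGATIONAL DRUG SUPPLY repeats this: "Select cases will be offered the opportunity to continue treatment through Week 52 on case-by-case basis".
- **Follow-up.** Tables 3 and 4 place the follow-up visits 4, 8, 12 and 16 weeks after the last dose, with GPG scored at each. Under PROCEDURES, a subject whose target-lesion GPG rises by at least one point in follow-up leaves the study.

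**The concern.** The analysis line does not match either endpoint as written. The second endpoint is a time, and nothing planned uses event times. The first is defined only after both healing and the end of drug, but the line allows the count to begin at healing alone, while infusions continue. A relapse on drug could then be reported as a relapse after stopping, which is a different clinical finding.

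Durability off drug is the main efficacy question for the four follow-up visits. If the start point, denominator and handling of incomplete follow-up are settled only after the data are seen, several different figures could be reported from the same 20 subjects under the same line of the plan.

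**Working it through.** The plan states no numerical figure for these two endpoints; its power statement concerns the primary endpoint only. The check is therefore a comparison of sections, followed by arithmetic on the visit schedule. Every event rate and loss rate below is an assumption, because the documents give none.

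**1. Endpoint against analysis**

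| | Recurrence endpoint | Worsening endpoint | Analysis line |
|---|---|---|---|
| Measure | occurrence | time | proportion |
| Starts at | healing of all lesions *and* cessation | cessation | healing *or* cessation, dated Week 28/26 |
| Subjects at risk | healed subjects | subjects who stop and are followed | not stated |
| Lesions | all | target | not stated |

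**2. Window length if the clock starts at healing**

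Inputs: last scheduled infusion at Week 28 (four-weekly) or Week 26 (three-weekly), and 16 weeks of follow-up after it.

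Total window = last infusion week + 16 − healing week. Part before the last infusion = last infusion week − healing week.

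- Four-weekly, healed at Week 4: 28 + 16 − 4 = 40 weeks, of which 28 − 4 = 24 precede the last infusion.
- Four-weekly, healed at Week 24: 28 + 16 − 24 = 20 weeks, of which 4 precede it.
- Three-weekly, healed at Week 14: 26 + 16 − 14 = 28 weeks, of which 12 precede it.
- From cessation, as the endpoint requires: 16 weeks for every subject with complete follow-up.

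**3. What that could do to the estimate**

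Let R be the assumed 16-week risk. If the hazard were constant and the same on and off drug, the risk over w weeks would be 1 − (1 − R)^(w/16).

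| R over 16 weeks | 20 weeks | 40 weeks |
|---|---|---|
| 20% | 24% | 43% |
| 40% | 47% | 72% |
| 60% | 68% | 90% |

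This is the unfavourable end. If no healed subject relapsed on drug, the count from healing would equal the count from cessation. For R = 40% and healing at Week 4, the figure therefore lies between 40% and 72%, depending on an on-drug relapse rate that the line does not separate out.

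**4. The Week 28/26 date**

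With extension, actual cessation can fall up to 52 − 28 = 24 weeks (four-weekly) or 52 − 26 = 26 weeks (three-weekly) after the stated date. Subjects discontinued during treatment stop before it.

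**5. Lost subjects**

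Assume visits at 4, 8, 12 and 16 weeks, R = 40%, and 20% independent loss over follow-up. Per interval:

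- event probability q = 1 − 0.60^(1/4) = 0.120
- loss probability c = 1 − 0.80^(1/4) = 0.054
- fraction staying at risk = (0.60 × 0.80)^(1/4) = 0.832

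Summing over four intervals, the multiplier is (1 − 0.48)/(1 − 0.832) = 3.10 before rounding. Observed events = q(1 − c) × 3.10 = 35.2%. Lost before any event = c × 3.10 = 16.8%.

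- Lost counted as no event: 35.2%
- Lost excluded: 35.2/(100 − 16.8) = 42.3%
- Lost counted as events: 35.2 + 16.8 = 52.0%
- Kaplan-Meier targets the true 40%

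Over true risks of 20–60% and losses of 10–30%, the errors run from about −11 to −1 points, +1 to +4 points, and +4 to +24 points respectively.

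**6. Scale ceiling**

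GPG runs from 0 to 4 (Appendix 1). Subjects who have neither improved nor significantly worsened stay on treatment to the end, so some may stop at 4 and cannot then register a one-point rise.

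**The case against.** The best defence is that the line is loosely worded and the intent is recoverable. It speaks of intervals in the plural, so it can be read respectively: recurrence from healing, worsening from cessation. The Week 28/26 parenthesis may simply name the usual last-dose visit, since all follow-up visits are timed from the last dose. Extension is for subjects whose wounds have not closed, so few of them would be in the healed group at Week 28. Only two secondary endpoints are involved, in a proof-of-concept trial of at most 20 subjects.

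Much of this stands, and it limits what can be said. A reader might infer the following, but the documents do not support it:

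- **That a proportion can estimate neither endpoint.** It is a sound summary of recurrence if restricted to healed subjects, started at cessation and given a fixed window.
- **That both outcomes are certainly merged into one figure.** That is one reading.
- **That lost subjects are counted as event-free.** No rule is given.
- **That 24 or 26 weeks on drug will be counted as time off drug for extension subjects.** That is the worst-case reading, and no number of such subjects is stated.
- **That the follow-up serves durability alone.** It also collects adverse events, quality of life, comorbidity status and cytokines.
- **That the GPG 4 ceiling comes from using a proportion.** It belongs to the scale, and Kaplan-Meier does not remove it.

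The defence does not reach the core. Even on the respective reading, recurrence starts at healing, when drug continues, and time to worsening is still reported as a proportion.

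**Conclusion.** The concern holds in a limited form. Two mismatches are plain from the text: a time endpoint with no time-to-event analysis, and a recurrence clock (healing *or* cessation) that contradicts its endpoint (healing *and* cessation). The Week 28/26 date also does not cover every subject, and the denominator and handling of lost subjects are unspecified.

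The certain part of the size is the schedule arithmetic: a window of up to 40 weeks without extension, 24 of them before the last infusion, where the endpoint calls for 16 weeks off drug. The effect on the reported percentage depends on unknown relapse and loss rates. Under the assumed rates it runs from nothing to tens of percentage points, and the bias from lost subjects can go in either direction.

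This should be corrected before analysis. It does not touch the primary endpoint or the sample size.

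**What to change.** Replace the single line with two analyses, both timed from each subject's actual last infusion, including any extension.

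1. **Time to worsening.** Event: a rise of at least one GPG point in the target lesion from its score when treatment stops. Use Kaplan-Meier over the 16-week follow-up, censored at the last GPG assessment, and report the 16-week estimate at the planned 90% level. Report how many subjects stop at GPG 4 and so cannot register a rise. State how subjects who stop early are handled.
2. **Recurrence.** Exact proportion (or Kaplan-Meier) among subjects with all lesions healed at cessation, over the same 16 weeks, with a stated rule for incomplete follow-up. GPG is scored for the target lesion only, so define healing of the other lesions from the recorded counts, measurements and photographs.

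Report relapses during treatment separately.

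The cost is SAP wording and slightly more analysis. GPG is already scored at every treatment, additional-treatment, follow-up and early-termination visit, so no new visit, test or subject is needed. The estimates will be imprecise with at most 20 subjects, and event times are known only to the nearest of four follow-up visits.

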Appendix 1. Clinician Assessment of Pyoderma Gangrenosum

At each visit, the following assessments will be performed:

1. Photographs of target PG ulcer (and other PG ulcers present)
2. Measure length, width, and depth target lesion

The following tools/questions have been adapted from various clinical studies for pyoderma gangrenosum and other dermatological conditions²²⁻²⁴.

Global Pyoderma Gangrenosum (GPG) Severity Score

Assess subject GPG severity of target lesion at each visit by using below categories

I. INFLAMMATION (adapted from Foss, C. et al 2008)¹

Ulcer Border Erythema	Point Value
None; possible residual hyperpigmentation	0
Slight: Pink to red color	1
Mild: Red color	2
Moderate: Deep red color	3
Severe: Violaceous/Grey	4

Ulcer Border Elevation	Point Value
None; flat border in plane with surrounding skin	0
Slight: border slightly elevated, <1 mm above ulcer base	1
Mild: Border noticeably elevated (1-2 mm) above ulcer base and surrounding skin	2
Moderate: Border significantly elevated above ulcer base (2-5mm)	3
Severe: Significant, rolled border >5 mm in any part of ulcer	4

Ulcer Purulence	Point Value
None: dry ulcer base	0
Slight Purulence 
• minimal to no purulent drainage• dressing is dry at presentation and dabbing lesion with 4x4 gauze does not appreciably wet the gauze.• No drops of purulence appreciated.	1

Mild Purulence 
 Few drops purulence appreciated upon examination. Dressings are damp at presentation and dabbing the wound with a 4x4 gauze wets the first layer of the gauze. 	2
Moderate Purulence 
 Ulcer bed covered with purulent drainage Dressings are wet at presentation and ulcer bed significantly wets a 4x4 gauze upon presentation. 	3
Severe Purulence 
 Necrotic tissue may be present Extensive purulent drops present on ulcer bed Dressings soaked at presentation and soaks 4x4 gauze when cleaned (can wet multiple 4x4 gauzes). 	4

II. RE-EPITHELIZATION

% Active Ulcer Base	Point Value
0% Active Ulcer	0
1%-25% Active Ulcer	1
26-50 % Active Ulcer	2
51-75% Active Ulcer	3
76-100% Active Ulcer	4

% Granulation Tissue	Point Value
Re-epithelization evident with cribiform scarring	0
More than 90% granulation tissue with some re-epithelization of skin evident	1
Mostly granulation tissue without any evidence of re-epithelization	2
Some evidence of granulation tissue; mostly purulent ulcer	3
No evidence of granulation tissue	4

III. PG ULCER Diameter

PG Ulcer Size	Point Value
No ulcer	0
Lesion measures greater than 0 cm and less than or equal to 2 cm	1
Lesion measures greater than 2 cm and less than or equal to 4 cm	2
Lesion measures greater than 4 cm and less than or equal to 6 cm	3
Lesion measures greater than 6 cm and less than or equal to 8 cm	4
Lesion measures greater than 8 cm and less than or equal to 10 cm	5
Lesion measures greater than 10 cm	6

Final Calculation

Sum of Points	Target Lesion GPG Severity Score & Ulcer Description
0-5	
Completely Clear: 0
 
 evidence of cribriform scarring, re-epithelization and possible residual hyperpigmentation. 0% ulceration apparent and lesion is dry
6-10	
Almost Clear: 1
 
 <25% of active ulceration present; more than 90% granulation tissue present with mild pink, slightly elevated borders. Some evidence of re-epithelization. Minimal to no purulent drainage at presentation; dressing is dry at presentation and dabbing lesion with 4x4 gauze does not appreciably wet the gauze. No drops of purulence appreciated.
11-15	
Mild: 2
 
 <50% of active ulceration with perceptible border elevation with mild red border. Evidence of granulation tissue without any re-epithelization of skin. Few drops purulence appreciated upon examination. Dressings are damp at presentation and dabbing the wound with a 4x4 gauze wets the first layer of the gauze.
16-20	
Moderate: 3
 
 <75% active ulceration with marked red, rolled borders and significant purulence. Some evidence of granulation tissue with multiple purulent drops and significant purulence on ulcer bed at presentation. Dressings are wet at presentation and ulcer bed significantly wets a 4x4 gauze upon presentation.
21-26	
Severe: 4
 
 100% active ulcer with violaceous, raised rolled borders. Necrotic tissue may be present. No evidence of granulation tissue. Extensive purulent drops present on ulcer bed. Dressings soaked at presentation and soaks 4x4 gauze when cleaned (can wet multiple 4x4 gauzes).

Appendix 2. Patient Pyoderma Gangrenosum Questionnaires

The following tools/questions have been adapted from various clinical studies for pyoderma gangrenosum and other dermatological conditions²².

Patient Reported- “Ooze” or Purulence Measure ²⁴

[figure not shown]
1. How often do you need to change your wound dressings in the past 4 weeks (circle the response that best applies to you)?
 - a. Multiple times per day
 - i. How many times? _____
 - b. Daily
 - c. Every other day
 - d. Every 3 days
 - e. Once a week
 - f. I do not use dressings
 - i. If you no longer require dressings, how many days after treatment did you stop placing dressings on your lesion (in days)? _____
 - ii. I have never used dressings for the ulcers
 - g. Other: _____

Patient Pain Visual Analogue Scale (VAS) ²²

Patients will be asked to report pain scores at each visit. Patients will report scores on a scale of 0 to 10.

0 signifies no pain and 10 signifies the worst pain imaginable. Choose an integer whole number.

DLQI (Dermatology Life Quality Index)

The scoring of each question is as follows:

Very much	scored 3
A lot	scored 2
A little	scored 1
Not at all	scored 0
Not relevant	scored 0
Question unanswered	scored 0

The DLQI is calculated by summing the score of each question. The maximum score is 30 and minimum score is 0. Higher score represents a quality of life that is more impaired.

Definition of DLQI Scores

21-30 = extremely large effect on patient's life

A change in DLQI score of at least 4 points is considered clinically important ²². Such change suggests that there has actually been a meaningful change in that patient's quality of life since the previous measurement of his/her/their DLQI scores.

Dermatology Life Quality Index

The aim of this questionnaire is to measure how much your skin problem has affected your life OVER THE LAST WEEK. Please check one box for each question.

1.	Over the last week, how itchy, sore, painful or stinging has your skin been?	Very much A lot A little Not at all	   	
2.	Over the last week, how embarrassed or self conscious have you been because of your skin?	Very much A lot A little Not at all	   	
3.	Over the last week, how much has your skin interfered with you going shopping or looking after your home or yard ?	Very much A lot A little Not at all	   	Not relevant 
4.	Over the last week, how much has your skin influenced the clothes you wear?	Very much A lot A little Not at all	   	Not relevant 
5.	Over the last week, how much has your skin affected any social or leisure activities?	Very much A lot A little Not at all	   	Not relevant 
6.	Over the last week, how much has your skin made it difficult for you to do any sport ?	Very much A lot A little Not at all	   	Not relevant 

7.	Over the last week, has your skin prevented you from working or studying ?	yes no	 	Not relevant 
	If "No", over the last week how much has your skin been a problem at work or studying ?	A lot A little Not at all	  	
8.	Over the last week, how much has your skin created problems with your partner or any of your close friends or relatives ?	Very much A lot A little Not at all	   	Not relevant 
9.	Over the last week, how much has your skin caused any sexual difficulties ?	Very much A lot A little Not at all	   	Not relevant 
10.	Over the last week, how much of a problem has the treatment for your skin been, for example by making your home messy, or by taking up time?	Very much A lot A little Not at all	   	Not relevant 

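### Unanswered DLQI items score 0 with no limit on how many, so an incomplete form reads as little or no impairment

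*Combined protocol and SAP*

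**What the plan says.** Appendix 2 (DLQI) introduces its scoring table with "The scoring of each question is as follows". The table gives *Very much* 3, *A lot* 2, *A little* 1, *Not at all* 0 and *Not relevant* 0. Its last row, "Question unanswered", also scores 0. The total is a plain sum: "The DLQI is calculated by summing the score of each question". The stated range is "The maximum score is 30 and minimum score is 0", and the direction is "Higher score represents a quality of life that is more impaired". The appendix adds a yardstick: "A change in DLQI score of at least 4 points is considered clinically important".

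Question 7 has a different format from the other nine. Its stem, "has your skin prevented you from working or studying", is answered yes, no or not relevant. A graded follow-up (*A lot*, *A little*, *Not at all*) applies only after *no*.

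The secondary endpoints include "Absolute change in quality of life (DLQI) from baseline at visits 3, 4, 5, 6, 7, 8, and 9" and at complete re-epithelization. Under Analysis of Secondary Endpoints, mean DLQI at baseline is compared by t-test with the means at Week 16 and at treatment termination. Neither Appendix 2 nor Statistical Considerations says how many unanswered items make a form unusable.

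**The concern.** On a scale where higher is worse, 0 is the best value an item can take. Giving that value to a blank treats not knowing as knowing that there is no impairment. With no limit, the rule extends to a form that is mostly or wholly blank, which then totals 0.

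The endpoint is a change from baseline, so the error depends on when the item was skipped. A skip at a later visit lowers the later total and looks like improvement. A skip at baseline lowers the starting point and conceals improvement. The trial has at most 20 subjects, no control arm, and a comparison of means before and after treatment. A few incomplete forms could therefore be visible in the result, and nothing in the plan would show that they were incomplete.

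The scoring table also does not reproduce the stated maximum, because *yes* to Question 7 has no listed score. That leaves one answer to the scorer's judgement.

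**Working it through.** **Inputs.** Item scores, the summing rule, the 0 to 30 range, the 4-point yardstick and the Question 7 layout are from Appendix 2. The number of subjects (20) is from Sample Size.

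**1. The plan's own maximum.** Nine questions (1 to 6 and 8 to 10) offer *Very much*: 9 × 3 = 27. The highest listed score on Question 7 is *no* followed by *A lot* = 2. The maximum from the table is 27 + 2 = 29, not 30. Giving *yes* each possible score in turn:

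| Score for *yes* | Maximum total |
|---|---|
| 0 | 27 + 2 = 29 |
| 1 | 27 + 2 = 29 |
| 2 | 27 + 2 = 29 |
| 3 | 27 + 3 = 30 |

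Only *yes* = 3 reproduces the stated 30.

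**2. Effect of skipped items on one subject.** Let S_B and S_F be the points that the skipped items would have earned at baseline and at follow-up. Then

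recorded change = true change + S_B − S_F.

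Each skipped item contributes between 0 and 3 points.

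| Items skipped on one form | Largest shift in the change | Reaches 4 points? |
|---|---|---|
| 1 | 3 | no |
| 2 | 6 | yes |
| 3 | 9 | yes |
| 4 | 12 | yes |

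The shift is negative (false improvement) when the skip is at follow-up and positive (hidden improvement) when it is at baseline. These are ceilings. They are reached only if every skipped item would have been answered with the worst response.

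**3. What a limit of one skip achieves.** With at most one unanswered item on each form, S_B and S_F each lie between 0 and 3. S_B − S_F then lies between −3 and +3. No subject's change can be shifted by as much as 4 points, even if one item is skipped at both visits.

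**4. Effect on the mean.** With 20 subjects, one subject with a false 6-point drop moves the mean change by 6 / 20 = 0.3 points. One with a false 3-point drop moves it by 3 / 20 = 0.15 points. The documents give no skip rate, so the total effect cannot be estimated.

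**The case against.** **Scoring a blank as 0 is an explicit rule fixed in advance, and nothing suggests that blanks will be common.** Both statements are true. The form has ten items and is completed at study visits by at most 20 subjects. The size of the problem is therefore unknown and may be small. But fixing a rule in advance does not make it sound, and this one has no point at which a form stops counting.

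**No planned analysis uses the 4-point threshold.** This also stands. DLQI is analysed as a difference in means, with no responder count, so a false important improvement in one subject would not itself be a reported result. The threshold serves here only as the protocol's own measure of what matters, and as a basis for where to set the limit.

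**The bias does not run one way.** Correct. A reader might infer that the rule favours the drug. That would require more skipping at follow-up than at baseline, and the documents give no reason to expect it.

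**Question 7.** A reader might infer that a subject prevented from working scores 0, below one for whom work is *a lot* of a problem, so that the item runs backwards. On that reading a move from *yes* to *A lot* counts as +2 (worse) instead of −1 (better). The mean change is off by 3 × (share answering *yes* at baseline − share at Week 16). With assumed shares of 10% to 50% at baseline and 0% to 25% at Week 16, that runs from 3 × (0.10 − 0.25) = −0.45 to 3 × (0.50 − 0) = +1.5 points. The documents do not support this reading. They are silent on *yes*; they do not score it 0. A subject who ticks *yes* has answered the question, and the graded line does not apply to that subject. The stated maximum of 30 also requires *yes* = 3. A row may simply be lost from the available text: of the severity bands on a 0 to 30 scale, only 21 to 30 appears there.

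**Conclusion.** The concern holds for unanswered items. Appendix 2 scores each of them as no impairment, without limit. This can shift a subject's change by up to 3 points for one skip and up to 6 for two. The direction depends on whether the skip is at follow-up or at baseline. These ceilings assume that the skipped items would have been answered *Very much*; the frequency is unknown.

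For Question 7 the finding is narrower: the table in the available text gives no score for *yes* and reaches 29 rather than 30. That calls for a clarification. It is not evidence that the most impaired subjects are scored as well.

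The matter is minor overall. It affects DLQI change, a secondary endpoint. The primary GPG endpoint and the sample size are untouched.

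**What to change.** In Appendix 2 and in the scoring program:

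- Set the DLQI total to missing when two or more of the ten items are unanswered. The cutoff follows from the protocol's own 4-point yardstick, as worked above.
- Keep 0 for *Not relevant*, and count it as an answer.
- State that *yes* to Question 7 scores 3, and that a *yes* with the graded line left blank is a complete answer. If the source document already has this row, only the second part is needed.
- Have site staff check each form for blanks before the subject leaves, and report how many totals were set to missing at each visit.

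The cost is a few lines of text and a small change to the program. The downside is that a few totals may become missing. A missing baseline total costs most, because it removes that subject from every DLQI change. The check at the visit is there to keep that number low. A single unanswered item would still score 0 and could still shift a change by up to 3 points.
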